5.3. Analysis of Primary Endpoint

For the primary analysis, we contrast the risk of diagnosed atopic dermatitis (AD) by two years of age for the intervention versus control groups under an intention-to-treat (ITT) assumption, analyzing all subjects according to the group to which they were allocated regardless of adherence or group crossover, and imputing missing outcome values using multiple imputation methods. The measure of interest is the ratio of the intervention:control proportions, a relative risk (RR) measure. If emollient use prevents AD, the RR will be significantly smaller than 1.

Estimation of the relative risk will be by log-binomial regression using a generalized linear model with a log link and binomial distribution. A binary indicator variable will represent assigned **study arm** (intervention=1, control=0). The exponentiated coefficient of this variable, $\exp(\beta_1)$, estimates RR. We will test $\beta_1 \neq 0$ at the 0.05 level of significance. If $p < 0.05$, we will consider RR significantly different from 1, meaning that there is strong evidence for the effect of emollient use on AD in very young children.

Stratification variables will also be included in the model to avoid bias in estimates of effects and standard errors. The stratification variables are **family history of atopy in a first-degree relative** and **recruiting clinic**, which will be included as a **random effect**. Because there are 45 recruiting

clinics in the study, clinic cannot be modelled as a fixed effect without losing statistical efficiency. No other baseline characteristics will be included.

Equation 1

$$\log(p[AD_{ij}]) = \beta_0 + \beta_1 Arm_{ij} + \beta_2 FamHx_{ij} + b_j$$

In this model, the variable *Arm* represents assigned **study arm** (intervention=1, control=0) for participant *i* recruited from clinic *j*. The variable *FamHx* represents family history of atopy in a first-degree relative (1/0). The term b_j is a random intercept for the primary care clinics where participants were recruited. The exponentiated intercept coefficient ($\exp(\beta_0)$) represents the cumulative prevalence of AD in the control arm, while $\exp(\beta_1)$ estimates RR.

Alternative strategies could be used to overcome convergence issues. If this model fails to converge, alternatives include substituting a Poisson model with robust variance estimates, providing starting values for estimation in the statistical software, or using an alternative algorithm.

Missingness in the primary outcome is addressed in detail the "Missing Data" section below. Consistent with the ITT assumption, if <5% of participants are missing the outcome variable, we will analyse this outcome under **multiple imputation** or using **Bayesian** methods as the primary approach.

In *reporting findings*, we will present the RR estimate with 95% confidence interval; if the outcome is imputed, both this and the complete case finding will be reported. We will also report the treatment effect as the absolute (rather than relative) risk difference. This can be calculated as the difference in the adjusted group prevalence using average conditional predicted risk. Standard errors (SE) and 95% confidence intervals can be obtained by the delta method, which is a standard method to compute SE of nonlinear transformations and can be executed using Stata's -margins- command, for example. The primary analysis will be repeated using raw (not model-based) estimates of risk and relative risk, to check for the influence of software defaults or model flaws on the findings.

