2.3. Sample Size and Recruitment Duration

1,250 parent/infant dyads (625 per arm) will be enrolled from 25 community-based family medicine and pediatric practices in four states (Oregon, Colorado, Wisconsin, and North Carolina). All parents/legal guardians, including males and females 18 years of age and older who meet inclusion/exclusion criteria are eligible for study participation. Recruitment is expected to take place over the course of 31 months; the time from start of recruitment until final two-year follow-up on all subjects is five years.

Power for Aim 1. For the purpose of the primary analysis, we include a sufficient number of babies in a 1:1 ratio for the two study arms to provide an overall type I error rate of 0.05 and 80% power to detect a 30% relative reduction in cumulative incidence of AD by two years of age (RR=0.7). In our planning grant, we determined the baseline cumulative incidence of AD in this age group and target clinics at 24%, which is consistent with recent population-based 2-year prevalence in the U.K.¹. Because our trials in high-risk populations of daily vs no emollient have shown reductions of 50%, we assume a more conservative 30% reduction to 16.8%. Using a test of two proportions, a total of 982 babies (491 per arm) are required to detect this difference. Allowing for an approximate 20%

¹ The screening questionnaire includes the question "Has at least one of your baby's blood-related PARENTS, BROTHERS OR SISTERS ever been diagnosed with asthma, eczema (atopic dermatitis) or hay fever (seasonal allergies)?" Strata are split at "Yes" responses vs. "No, or don't know."

loss to follow-up, we plan to enroll 1,250 babies (625 per arm). Sample size calculations were performed using Stata/IC version 16.1.

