3.6. Analysis Populations

The **Intention-to-Treat (ITT) Population** will contain all randomized participants. Missing outcomes will be multiply imputed to reduce bias without exaggerating precision per recommendations by Little and Yau for longitudinal studies³.

The **Complete Case Population** will include the subset of participants with non-missing primary outcomes.

The **Per-Protocol Population** will assign participants who report emollient use to the intervention arm (regardless of randomization), and those who report no emollient use to the control arm. This dataset will be used to estimate the relationship between frequency of emollient use and AD.

The **Safety Population** includes all randomized participants. Safety outcomes are reviewed regularly by the DSMB.

The **AD Population** includes children with diagnosed AD (chart review).

4. Trial Population

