5.1. Statistical Hypotheses and Outcome Definitions

1. Our primary hypothesis is that the intervention will result in significantly **lower cumulative incidence of provider-diagnosed AD by age 24 months**.

After two years of follow-up, we will calculate the proportions of children diagnosed with AD by trained primary care providers in the intervention and control arms. Clinicians will be trained in pediatric AD standard diagnosis criteria.⁴ As our primary analysis, we will test the hypothesis that the ratio of the intervention:control proportions, a relative risk (RR) measure, is significantly smaller than 1 with a two-sided test: **RR ≠ 1 vs RR= 1**. This analysis will be conducted in an intention-to-treat (ITT) analysis dataset of all randomized participants with multiple imputation for missing outcomes.

Provider-diagnosed AD, the current gold standard, will be recorded during chart abstraction and referred to as **GS-AD**. The case report form (CRF) includes a question:

Was there a diagnosis of AD (includes eczema, atopic eczema, atopic dermatitis, and neurodermatitis)? with forced choice responses:

- 1, Yes
- 0, No / No documentation
- 2, Not sure / Possible - AD diagnosis is not confirmed

The CRF further elaborates:

To check "Yes", there must be an official diagnosis from a provider. If a provider is considering eczema as a possibility, or if a parent thinks the child has eczema, mark "Not Sure/Possible" and provide verbatim description from the medical record. Choose "Not sure/Possible" if there is some evidence of eczema but no official diagnosis.

All "not sure/possible" records and their explanatory notes will be reviewed by the principal investigator or dermatology physician co-investigators under blinding before the dataset is locked for analysis. Fields describing the presence and date of onset of similar or comorbid conditions-- such as candida of the skin, impetigo, and molluscum--are part of this record. Parent responses to the Childhood Eczema Questionnaire^{5,6} (CEQ) (see item 2c below) will also be available for review during this determination.

After this review, any child with a "Yes" response or adjudicated as probable AD by physician reviewers will be considered to have AD and the outcome variable will be set to equal 1. "No" and "Not sure" responses adjudicated as not probable AD will be considered not AD and the outcome will be set to 0.

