5.9. Missing Data

The approach to missing data will be guided by sources such as Jakobsen et al²¹ on missing data in randomized trials.

Definition of missingness in the primary outcome: The primary outcome, AD by 24 months of age, will be ascertained through review of medical records by research personnel blinded to intervention status and will be considered *not missing* if either (1) a diagnosis of AD is found for any visit before age 24 months (± 3 months), *or* (2) no diagnosis is found *and* the child had at least one visit in the 24-month window. The outcome will be considered missing if those conditions are not met, i.e. we

find no diagnosed AD before age 2 years *and* no clinic visit within ± 3 months of the child's second birthday.

COVID-19 pandemic as a cause of missingness: Because the primary outcome depends on an in-person clinic visit, it is likely to be missing for children who would otherwise have had visits during periods when the clinic was not offering in-person care or when parents declined to bring children for non-urgent care. The study team discussed extending the window for chart reviews to mitigate this effect, but this would require contacting parents for consent and was not adopted.

Missingness in other variables: Other variables from parent report will be considered missing if the response is absent or "don't know/unsure" or similar. In chart reviews, missingness will occur if a visit is not found, but if a visit is found, a "not found" for a particular category (e.g. medication) will be considered a non-missing "no." Validated multi-item scales will be scored according to published guidelines when available. When guidelines are not available, decisions about how to treat missing responses will be made and recorded before the dataset is locked for analysis.

If $\leq 5\%$ of observations are missing the primary outcome, then multiple imputation methods will not be of benefit and we will perform analysis without imputation. The treatment assignment, family history of atopic dermatitis, and recruiting clinic are assigned or used to create arm assignments and so will be complete for all participants.

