If $>5\%$ of observations are missing outcomes, then further steps are needed. In addition to the analytic steps described here, we will discuss with members of the study team who interact with participants and clinic staff and may have insight into reasons for loss to follow-up that may or may not be reflected in recorded data. As a first step, we will create an indicator variable $R=1$ if the outcome is missing, $R=0$ if not missing. This variable R can be used to test whether missingness is associated with other variables, particularly:

- Study arm
- Family history of atopy
- Date of enrollment in study
- Parent report of AD
- Child's Eczema Questionnaire (CEQ) signs of AD
- UK Working Party criteria for AD
- PBRN

If differences are found (at $p < 0.10$, approximately, for an inclusive approach) then covariate-dependent missingness at least partly explains the missingness mechanism. Any such variable should be used in the multiple imputation model (or included in the main model without imputation) to produce unbiased estimates.

Multiple imputation will be performed using iterative chained equations over five (5) imputation sets. At the time of writing, the performance of multiple imputation when the model includes a random effect, such as the recruiting clinic in our model, is not well understood, and software to run the model we have proposed under multiple imputation is not readily available. (The estimation command is not available in Stata version 16, for example). Alternatives include (a) substituting a Poisson or logistic model, (b) omitting clinic, which should not be strongly associated with treatment outcome, or (c) Bayesian approaches, which could be especially useful if we suspect that data are missing not at random. The multiple imputation results will be considered the primary findings and will be reported along with complete case analysis.

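### SAP 5.3 reverses the 5% missing-outcome rule of SAP 5.9, and the imputation model and number of imputations in 5.9 can be strengthened at almost no cost

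*SAP*

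**What the plan says.** The SAP gives three versions of the rule for missing primary outcomes.

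- **SAP 5.3, paragraph on missingness:** "if <5% of participants are missing the outcome variable, we will analyse this outcome under" multiple imputation or Bayesian methods, as the primary approach. The same paragraph sends the reader to the Missing Data section for detail.
- **SAP 5.9:** at 5% missing or less, "then multiple imputation methods will not be of benefit and we will perform analysis without imputation". Above 5%, further steps apply, and "The multiple imputation results will be considered the primary findings and will be reported along with complete case analysis".
- **No threshold:** SAP 3.6 ("Missing outcomes will be multiply imputed to reduce bias without exaggerating precision"), SAP 5.1 ("all randomized participants with multiple imputation for missing outcomes") and the first paragraph of SAP 5.3 ("imputing missing outcome values using multiple imputation methods"). Protocol 10.4.1 also imputes with no threshold.

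On the imputation model, SAP 5.9 tests a missingness indicator against a list that includes study arm, family history, parent-reported AD, CEQ and UK Working Party status. Variables associated at about p<0.10 are to be used. Protocol 10.4.1 names arm, clinic and parent-reported diagnosis as imputation variables with no such screen. SAP 5.9 sets five imputations.

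**The concern.** The threshold that selects the primary analysis should read one way before the blind is broken. Here one sentence inverts it. Below 5% missing, 5.3 and 5.9 direct the analyst to different primary results; above 5%, that sentence of 5.3 gives no rule.

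Two further features of 5.9 are valid but weaker than they need be.

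- **Imputation variables.** The only stated entry rule is association with missingness. If missingness is balanced between arms, which is the good outcome, an analyst who treats the screen as the sole gate would leave arm out. Imputed children in both arms would then be drawn from a common risk, which pulls the RR toward 1.
- **Five imputations.** At about 20% missing, the result carries enough simulation noise that a p-value near 0.05 can fall on either side depending on the seed.

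**Working it through.** **1. The rules side by side**

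| Place | At or below 5% missing | Above 5% missing |
|---|---|---|
| SAP 5.3, missingness paragraph | Imputation or Bayesian is primary (strictly below 5%) | No rule |
| SAP 5.9 | No imputation | Imputed result is primary |
| SAP 3.6, 5.1, first paragraph of 5.3; protocol 10.4.1 | Impute | Impute |

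**2. The plan's own figures (SAP 2.3).** Inputs: 24% vs 16.8%, two-sided 0.05, 80% power, 1:1.

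n per arm = [1.96·√(2·0.204·0.796) + 0.8416·√(0.24·0.76 + 0.168·0.832)]² / 0.072² = 491, total 982. This matches the SAP. Planned loss of about 20% is 0.20 × 1,250 = 250 infants; the 5% line is 0.05 × 1,250 = 62.5. The trial expects to be far above the line.

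**3. Effect of the contradiction.** With 625 per arm and 4% missing unrelated to AD, the imputed result (five imputations, arm in the model) and the complete-case result differ on p<0.05 in about 1.5 to 1.7% of simulated trials. Under the SAP 5.9 definition of missingness, with 4.2 to 4.5% missing, the figure is 1.5 to 1.6%.

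**4. Leaving arm and all AD proxies out of the imputation model**

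*Scenario A: 20% missing, unrelated to AD.* Pooled risk = (0.24 + 0.168)/2 = 0.204.

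RR = (0.8·0.168 + 0.2·0.204)/(0.8·0.24 + 0.2·0.204) = 0.1752/0.2328 = 0.753.

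The same formula gives 0.726 at 10% missing and 0.780 at 30%. With arm in, the RR is 0.70.

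*Scenario B: the SAP 5.9 definition.* An outcome is missing only if no AD is charted and there is no visit in the 24-month window. Assume 25% have no such visit and a share f of AD is charted earlier. With f = 0.5:

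- Missing: control 0.25·(1 − 0.5·0.24) = 0.220; intervention 0.25·(1 − 0.5·0.168) = 0.229.
- Observed AD: control 0.24·0.875 = 0.210; intervention 0.168·0.875 = 0.147.
- Arm in: (0.147/0.771)/(0.210/0.780) = 0.708.
- Arm out: pooled observed risk = 0.357/1.551 = 0.230; RR = (0.147 + 0.229·0.230)/(0.210 + 0.220·0.230) = 0.766.

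With f = 0.8 the RR is 0.713 with arm in and 0.766 with arm out.

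*Power.* 40,000 simulated trials per scenario, Rubin's rules on log RR:

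| | Arm in | Arm and proxies out |
|---|---|---|
| A, m=5 | 77% | 62% |
| A, m=50 | 80% | 65% |
| B, m=5 | 79–82% | 63–68% |
| B, m=50 | 82–85% | 66–71% |

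*How often the screen would admit each variable.* Arm passes at 0.10 in 10% of trials in A and 12–17% in B. In B, parent report passes in 65–97% if half the children have one and 89–100% if all do.

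*Parent report in, arm out* (A, m=5, 20,000 trials, assumed sensitivity 0.8 and specificity 0.9): RR 0.740 and power 70% (81% with arm in) if half have a report; RR 0.728 and power 77% (83% with arm in) if all do.

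**5. Number of imputations.** Take the fraction of missing information as 0.20. Relative efficiency is 1/(1 + 0.20/m): 0.962, 0.990 and 0.996 at m = 5, 20 and 50. The seed-to-seed SD as a share of the SE is √(0.20/m): 20%, 10% and 6%. In simulation, with arm in and each trial imputed twice:

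| | m=5 | m=20 | m=50 |
|---|---|---|---|
| A: power | 77.4% | 79.6% | 79.8% |
| A: two seeds disagree on p<0.05 | 9.5% | 3.8% | 2.3% |
| B: power | 79–82% | 82–84% | 82–85% |
| B: two seeds disagree | 9–10% | 3–4% | 2% |
| A with parent report: two seeds disagree | 6–7% | 3% | 1.5–2% |

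**The case against.** The strongest reply is that '<5%' is a plain slip. The paragraph points to 5.9, which alone gives a reason; planned loss is four times the line; and complete-case, best-case, worst-case and tipping-point analyses are already planned. All of this is true, and it makes the effect small. It does not remove the conflict in the rule that picks the primary result.

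On the imputation model, the screen is described as inclusive and excludes nothing, and protocol 10.4.1 names arm outright. That also stands: harm arises only if the screen is read as the sole gate. The figures with arm and every proxy out are the extreme case, because parent report would often pass. With parent report in and arm out in scenario B (m=5, 2,500 trials per setting, same assumed accuracy), the RR is 0.735 to 0.754 and power 70–79%, against 81–85% with arm in. The loss is smaller, about 5 to 11 points, but real.

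Including CEQ and UK Working Party has some cost. Both come from annual questionnaires, will themselves be missing for non-responders, and share their first two items, so they also need imputing and may be collinear.

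Five imputations are valid under Rubin's rules, and the power gain from more is only about 1 to 3 points. The case for more rests on repeatability.

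**Conclusion.** The contradiction is established from the current SAP text and should be corrected before the blind is broken. Its practical effect is small: at most about 1.7% of verdicts at 4% missing, and little at the planned 20%, where the other sections agree on imputation.

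The two points about 5.9 are improvements, not errors. Guaranteeing arm is the more valuable: it rules out a shift in RR from 0.70 to about 0.75 (0.71 to 0.77 under the SAP's own missingness definition) and a power loss of up to about 17 points. More imputations cut seed dependence from roughly one trial in ten to about one in forty or fewer.

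These sizes rest on 24% vs 16.8%, 625 per arm, and the stated missingness scenarios. The 25% without a 24-month visit, the 50–80% of AD charted earlier, and the availability and accuracy of parent report are assumptions; the documents do not give them.

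**What to change.** 1. In the missingness paragraph of SAP 5.3, change '<5%' to '>5%'. Add 'as set out in 5.9' to SAP 3.6, 5.1 and the first paragraph of 5.3, and note that 5.9 replaces the imputation without a threshold in protocol 10.4.1. This aligns the threshold only. It does not choose between imputation and the Bayesian option in 5.3, or among the fallback models in 5.9.
2. In SAP 5.9, state that the imputation model always contains study arm, clinic (or PBRN), family history, parent-reported AD, CEQ and UK Working Party status. Use the p<0.10 screen only to add variables. Either add the other imputation variables named in protocol 10.4.1 (risk factors, emollient use, significant Aim 2 interactions) or say they are not carried over.
3. Raise the number of imputations from 5 to about 50 (20 gives most of the gain) and state the seed in advance. The larger number reduces dependence on the seed; stating the seed only makes the result reproducible.

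Cost: one character and a few words for the first, a few sentences for the second, and a few minutes of computing for the third. No new data are needed.

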5.4. Analysis of the Secondary Endpoints

Definitions of secondary endpoints are in section 5.1

The following **binary outcomes** will be evaluated with log-binomial models similar to Equation 1 for the primary outcome. When comparing intervention versus controls, we will use a Wald test for the intervention regression coefficient at the 0.05 level of significance.

2. As secondary/sensitivity analyses, we will test the intervention effect with alternative definitions of AD at 24 months, namely:
 - a) Complete case analysis of the primary endpoint (GS-AD), provider diagnosis, adjusting for stratification variables as well as covariates that we find to be associated with missing AD status;
 - b) PR-AD- Parent report of a provider diagnosis at any point in the ITT dataset;
 - c) UK Working Party in the ITT dataset;
 - d) CEQ-AD- Children's Eczema Questionnaire (CEQ) in the ITT dataset;

3. Cumulative incidence of AD at 18 months.

In addition to the binary models, we will conduct a multivariate or latent variable analysis to estimate cumulative incidence in each treatment arm using multiple candidate definitions and estimating the correlations between the definitions.

4. Cumulative incidence of AD treated with prescription and/or over-the-counter medication(s)

- a) Clinically-significant severe AD (CS1-AD)
- b) Clinically-significant moderate to severe AD (CS2-AD)

Non-AD (but still binary) outcomes include the following:

5. Probable or predicted asthma by the modified Asthma Predictive Index, and/or symptoms of asthma such as wheezing or prescribed bronchodilator.

6. Food allergy, defined by:

- a) Parental report of provider diagnosis of food allergy
- b) Positive prick testing or IgE blood test
- c) Parental report of immediate food allergy symptoms
- d) Near definite FA- provider diagnosis, positive test, and immediate symptoms

7. Prescription topical medication use or over-the-counter hydrocortisone use in (1) the ITT dataset, and (2) the AD dataset

- a) reported by parent
- b) identified during chart review

For **continuous** outcomes, use histograms and normal quantile plots to check for obvious lack of symmetry. Test for group differences with a linear regression model similar to the log-binomial models described above, using bootstrapped standard errors if the distribution of responses is non-normal.

8. In the AD dataset, severity of symptoms as measured by:

- a) Mean Patient-Oriented Eczema Measure (POEM) (a) averaged and (b) summed across all items in the ITT dataset.
- b) Mean score on the 30-point Infants' Dermatitis Quality of Life Index (IDQOL) summed across items in the ITT dataset

Age at onset will be tested using either pooled logistic regression or time-to-event methods for interval-censored data. For these analyses, age of onset will be indexed to the quarterly contact when the parent reported a diagnosis or to the closest corresponding age if the first diagnosis date is in the child's medical chart. Although we may not have sufficient sample size to detect an age-dependent treatment effect, it is possible that the greatest protective effects will be observed at early ages. Kaplan-Meier curves or similar visualizations may help to evaluate differences in treatment effect by age of onset.

9. Age of onset to the nearest 3 months determined by

- a) parental report of eczema from quarterly contacts or annual questionnaires
- b) provider-recorded date of first diagnosis retrieved from record review of chart by research coordinator indexed to the nearest quarter of follow-up

Mean days of disrupted sleep will be treated as a **count** variable and tested with a Poisson model similar to those described above.

10. Lower mean days of disrupted sleep in the past week for infants reported by parents at
 - a) 12 months
 - b) 24 months

